5.2 ASSESSMENT OF SAFETY

5.2.1 Physical examination

A complete physical examination will be performed at the time points specified in the flowchart. It includes at a minimum general appearance, neck, lungs, cardiovascular system, abdomen, extremities, and skin.

Measurement of height and body weight will be performed at the time points specified in the flowchart.

The results must be included in the source documents available at the site.

5.2.2 Vital signs

Vital signs will be evaluated at the time points specified in the flowchart, prior to blood sampling.

Vital signs (supine and standing systolic and diastolic blood pressure and pulse rate) and weight will be measured throughout the study. The blood pressure and pulse rate will be determined after 5 minutes of quiet rest in supine position and after 1 minute in the standing position. The incidence of symptomatic and asymptomatic orthostatic hypotension will also be tabulated for each visit. Symptomatic orthostatic hypotension should be recorded as an Adverse Event (AE).

5.2.3 Safety laboratory parameters

Safety laboratory parameters to be assessed are listed in Table 5.2.3:1. For the sampling time points please see the [flow chart](#).

All analyses will be performed by the local laboratory of each site, and the respective reference ranges will be collected and filed in the ISF.

Patients have to be fasted for the blood sampling for the safety laboratory.

It is the responsibility of the investigator to evaluate the laboratory reports. The significant abnormality as judged by the investigator will be reported as adverse events (please refer to [Section 5.2.6](#)).

Table 5.2.3:1 Safety laboratory tests

Category Test name	Category Test name
Haematology	Haematocrit, haemoglobin, erythrocyte count, white blood cell count (total and differential: lymphocytes, monocytes, neutrophils, eosinophils, basophiles), platelet count.
Serum chemistry	Urea, uric acid, creatinine, protein (total), albumin, aspartate aminotransferase (AST), alanine aminotransferase (ALT), gamma glutamyl transferase (GGT), alkaline phosphatase, total bilirubin, sodium, potassium, chloride, glucose, total cholesterol, triglycerides.

5.2.4 Electrocardiogram

The 12-lead ECGs will be recorded as scheduled in the flowchart. The investigator or a designee will evaluate whether the ECG is normal or abnormal and whether it is clinically relevant, if abnormal. ECGs may be repeated for quality reasons and the repeated recording used for study.

Additional ECGs may be recorded for safety reasons. Dated and signed printouts of ECG with findings should be documented in patient's medical record.

Clinically relevant abnormal findings will be reported either as baseline condition (if identified at the screening visit) or otherwise as adverse events and will be followed up and/or treated as medically appropriate.

5.2.5 Other safety parameters

Modified Minnesota Impulsive Disorders Interview (MMIDI) [[R06-1142](#)].

The MMIDI is a semi-structured clinical interview designed to assess a number of impulse control disorders. This scale will be completed to evaluate impulse control disorders which

may potentially occur in patients treated with Pramipexole. The instrument has been modified by Boehringer-Ingelheim to focus on compulsive behaviours which may occur in this patient population (pathological gambling, compulsive buying and compulsive sexual behaviour).

The other behaviours included in the MMIDI will not be assessed.

The MMIDI asks a series of questions to the patient and tabulates the total score as a measure of the probability for impulsivity. Each item is scored either “No” or “Yes”.

The MMIDI will be completed at visit 2 (week 0), visit 5 (week 8), visit 7 (week 18) and visit 8 (follow-up). In case the patient experiences any abnormal behavior at visit 3 (week 2), visit 4 (week 4) and visit 6 (week 12), then the Modified MIDI sub-scale has to be completed. In addition, at each other on-site visit, the investigator will ask the patient the following question: “Since the last visit, did you experience any of the following abnormal behaviours: Pathological gambling? Compulsive buying? Compulsive sexual behavior?” In case any of these questions is answered “Yes”, then MMIDI interview for relevant sub-scale(s) will be performed.

5.2.6 Assessment of adverse events

5.2.6.1 Definitions of AEs

Adverse event

An adverse event (AE) is defined as any untoward medical occurrence in a patient or clinical investigation subject administered a medicinal product and which does not necessarily have to have a causal relationship with this treatment.

An AE can therefore be any unfavourable and unintended sign (including an abnormal laboratory finding), symptom, or disease temporally associated with the use of a medicinal product, whether or not considered related to the medicinal product.

Serious adverse event

A serious adverse event (SAE) is defined as any AE which fulfils at least one of the following criteria:

- results in death,
 - is life-threatening, which refers to an event in which the patient was at risk of death at the time of the event; it does not refer to an event that hypothetically might have caused death if more severe.
 - requires inpatient hospitalisation or
 - requires prolongation of existing hospitalisation,
 - results in persistent or significant disability or incapacity, or
 - is a congenital anomaly / birth defect,
- or
- is deemed serious for any other reason if it is an important medical event when based on appropriate medical judgement which may jeopardise the patient and may require medical or surgical intervention to prevent one of the other outcomes listed in the above definitions. Examples of such events are intensive treatment in an emergency room or at home for allergic bronchospasm, blood dyscrasias or convulsions that do not result in hospitalisation or development of dependency or abuse.

AEs considered “Always Serious”

Cancers of new histology and exacerbations of existing cancer must be classified as a serious event regardless of the duration between discontinuation of the drug and must be reported as described in [5.2.6.2](#), subsections “AE Collection” and AE reporting to sponsor and timelines” In accordance with the European Medicines Agency initiative on Important Medical Events, Boehringer Ingelheim has set up a list of further AEs, which by their nature, can always be considered to be “serious” even though they may not have met the criteria of an SAE as defined above.

The latest list of “Always Serious AEs” can be found in the Electronic Data Capture (EDC) system. These events should always be reported as SAEs as described above.

Adverse events of special interest (AESIs)

The term AESI relates to any specific AE that has been identified at the project level as being of particular concern for prospective safety monitoring and safety assessment within this trial, e.g. the potential for AEs based on knowledge from other compounds in the same class. AESIs need to be reported to the sponsor’s Pharmacovigilance Department within the same timeframe that applies to SAEs, please see above.

No AESIs have been defined for this trial.

Intensity (severity) of AEs

The intensity (severity) of the AE should be judged based on the following:

Mild:	Awareness of sign(s) or symptom(s) that is/are easily tolerated
Moderate:	Sufficient discomfort to cause interference with usual activity
Severe:	Incapacitating or causing inability to work or to perform usual activities

Causal relationship of AEs

Medical judgement should be used to determine the relationship, considering all relevant factors, including pattern of reaction, temporal relationship, de-challenge or re-challenge, confounding factors such as concomitant medication, concomitant diseases and relevant history.

Arguments that may suggest that there is a reasonable possibility of a causal relationship could be:

- The event is consistent with the known pharmacology of the drug.
- The event is known to be caused by or attributed to the drug class.
- A plausible time to onset of the event relative to the time of drug exposure.
- Evidence that the event is reproducible when the drug is re-introduced
- No medically sound alternative aetiologies that could explain the event (e.g. pre-existing or concomitant diseases, or co-medications).
- The event is typically drug-related and infrequent in the general population not exposed to drugs (e.g. Stevens-Johnson syndrome).
- An indication of dose-response (i.e. greater effect size if the dose is increased, smaller effect size if dose is diminished).

Arguments that may suggest that there is no reasonable possibility of a causal relationship could be:

- No plausible time to onset of the event relative to the time of drug exposure is evident (e.g. pre-treatment cases, diagnosis of cancer or chronic disease within days / weeks of drug administration; an allergic reaction weeks after discontinuation of the drug concerned)
- Continuation of the event despite the withdrawal of the medication, taking into account the pharmacological properties of the compound (e.g. after 5 half-lives). Of note, this criterion may not be applicable to events whose time course is prolonged despite removing the original trigger.
- Additional arguments amongst those stated before, like alternative explanation (e.g. situations where other drugs or underlying diseases appear to provide a more likely explanation for the observed event than the drug concerned).
- Disappearance of the event even though the trial drug treatment continues or remains unchanged.

5.2.6.2 Adverse event collection and reporting

AE Collection

The investigator shall maintain and keep detailed records of all AEs in the patient files.

The following must be collected and documented on the appropriate CRF(s) by the investigator:

- From signing the informed consent onwards until the individual patient's end of trial:
-all AEs (serious and non-serious).
- After the individual patient's end of trial:
the investigator does not need to actively monitor the patient for AEs but should only report related SAEs of which the investigator may become aware of by any means of communication, e.g. phone call. Those AEs should however, not be reported in the CRF.

[figure not shown]

Figure 5.2.6.2: 1 adverse event collection and reporting

AE reporting to sponsor and timelines

The investigator must report SAEs and non-serious AEs which are relevant for the reported SAE, on the BI SAE form via fax immediately (within 24 hours) to the sponsor's unique entry point and local PV China (country specific contact details will be provided in the ISF). The same timeline applies if follow-up information becomes available. In specific occasions the investigator could inform the sponsor upfront via telephone. This does not replace the requirement to complete and fax the BI SAE form.

With receipt of any further information to these events, a follow-up SAE form has to be provided. For follow-up information the same rules and timeline apply as for initial information.

Information required

For each AE, the investigator should provide the information requested on the appropriate eCRF pages and the BI SAE form, if applicable. The investigator should determine the causal relationship to the trial medication and any possible interaction between the trial medication and a Non-Investigational Medicinal Product (NIMP).

The following should also be recorded as an (S) AE in the CRF and BI SAE form (if applicable):

- Worsening of the underlying disease or of other pre-existing conditions
- Changes in vital signs, ECG, physical examination and laboratory test results, if they are judged clinically relevant by the investigator.

If such abnormalities already pre-exist prior to trial inclusion they will be considered as baseline conditions and should be collected in the eCRF only. All (S)AEs, including those persisting after individual patient's end of trial must be followed up until they have resolved, have been assessed as "chronic" or "stable", or no further information can be obtained.

Pregnancy

In rare cases, pregnancy might occur in a clinical trial. Once a patient has been enrolled in the clinical trial and has taken trial medication, the investigator must report any drug exposure during pregnancy in a trial participant immediately (within 24 hours) by means of Part A of the Pregnancy Monitoring Form to the sponsor's unique entry point.

Similarly, potential drug exposure during pregnancy must be reported if a partner of a male trial participant becomes pregnant. This requires a written consent of the pregnant partner.

The outcome of the pregnancy associated with the drug exposure during pregnancy must be followed up and reported to the sponsor's unique entry point on the Pregnancy Monitoring Form for Clinical Trials (Part B).

The ISF will contain the Pregnancy Monitoring Form for Clinical Trials (Part A and B).

As pregnancy itself is not to be reported as an AE, in the absence of an accompanying SAE, only the Pregnancy Monitoring Form for Clinical Trials and not the SAE form is to be completed. If there is an SAE associated with the pregnancy an SAE form must be completed in addition.

5.3 DRUG CONCENTRATION MEASUREMENTS AND PHARMACOKINETICS

5.3.1 Assessment of pharmacokinetics

Not applicable.

5.3.2 Methods of sample collection

Not applicable.

5.3.3 Analytical determinations

Not applicable.

5.3.4 Pharmacokinetic – pharmacodynamic relationship

Not applicable since no pharmacodynamics data will be collected or analysed in this trial.

5.4 ASSESSMENT OF BIOMARKER(S)

Not applicable since no biomarker data will be collected and analysed in this trial.

5.4.1 Biobanking

Not applicable since no sample will be collected and analysed for biobanking in this trial.

5.5 OTHER ASSESSMENTS

Demographics, Height and Baseline Conditions: Demographics details, height and baseline conditions will be documented.

Medical History: Medical history will be collected to assess the qualification of subjects (including PD and concomitant diseases, if applicable).

Modified Hoehn and Yahr scale [[R02-0836](#)]: Modified Hoehn and Yahr scale will be completed at on-time. Stages of the Parkinson's disease will be assessed on 8 degrees between stage 0 (no sign of disease) to stage 5 (wheelchair bound or bedridden unless aided) in steps of 0, 1, 1.5, 2, 2.5, 3, 4 and 5.

Patient Diary: The cumulative hours of off-time every day during waking hours will be documented on a patient diary completed for 2 consecutive days before randomization visit.

Mini-Mental State Examination (MMSE) [[R96-2656](#)]: The MMSE is a patient reported instrument which evaluates orientation, memory, attention, concentration, naming, repetition, comprehension, ability to create a sentence, and ability to copy two intersecting polygons. A lower score indicates more cognitive impairment.

Urine Pregnancy Test: In women of childbearing potential, urine will be taken for pregnancy tests.

Concomitant Therapy (start date, end dates and changes): Concomitant therapy related to PD will be collected at least 3 months prior to randomization visit which should be recorded in the eCRF. All the concomitant therapy should be recorded in the eCRF starting from the date of signing study informed consent, and ending at the follow up visit. After the follow up visit, only concomitant therapy indicated for treatment of an AE has to be reported.

Compliance: The investigator will be responsible for the assessment of patient compliance to study drug (see also [section 4.3](#)).

5.6 APPROPRIATENESS OF MEASUREMENTS

NHQ will be used to evaluate the severity of nocturnal hypokinesia which was not covered by SCOPA scale. It is considered as a “non standard” criterion.

The EMO will be used to evaluate the bodily movements when patient wakes up in the morning. It is considered as a “non standard” criterion.

The rest of efficacy and safety criteria evaluated in this study are conventionally used in PD clinical trials. None of them could be considered as a "non standard" criterion.

6. INVESTIGATIONAL PLAN

6.1 VISIT SCHEDULE

The time window of all visits has been outlined in the [Flow Chart](#).

If a patient does not appear to a visit, all efforts should be made to contact the patient. If a visit is conducted outside of the planned time interval, further process should be discussed with the sponsor.

6.2 DETAILS OF TRIAL PROCEDURES AT SELECTED VISITS

6.2.1 Screening period

Screening Period – visit 1

- Obtain written informed consent
- Assign patient number
- Obtain comprehensive medical history and demographics to determine eligibility according to inclusion/exclusion criteria
- Perform comprehensive physical examination (including heart, lungs, abdomen, extremities, height and weight, etc.) including also a skin examination
- Obtain vital signs (blood pressure, pulse rate measurements), weight and height
- Perform MMSE
- Perform a Modified Hoehn & Yahr Scale staging at on-time
- Review inclusion/exclusion criteria
- Instruct the patient how to complete the diary and supply the patient with one. The diary will be collected and reviewed at visit 2
- Collect fasted blood sample for safety laboratory evaluation
- Perform spot urine pregnancy test (for females with childbearing potential)
- Perform a 12-lead ECG
- Record concomitant therapies including PD therapies
- Record any AE which might have occurred during the screening visit, after the informed consent was signed (e.g. if a patient gets a bleeding at the puncture site when the blood is drawn for the screening lab test)
- Instruct and supply health economics questionnaire
- Supply trial identification card

6.2.2 Treatment period(s)

6.2.2.1 Randomization visit (visit 2) at day 0

If the patient still qualifies for the study the following assessments are provided by the investigator:

Visit 2 (Randomisation visit) at day 0:

- Obtain vital signs (blood pressure, pulse) and weight
- Collect and review the completed patient diary. Check that the patient diary has been accurately completed, i.e. that there are no more than 4 double or missing entries on either day.
If there are more than 4 double or missing entries on one day, no other activities or ratings should be done, i.e. the patient is not eligible for baseline evaluation. Another attempt to obtain a valid baseline diary can be undertaken and the randomization visit rescheduled.
If the diary has been accurately completed (i.e. no more than 4 double or missing entries on either day), documented on a patient diary completed for 2 consecutive days before randomization visit, the patient can be randomized.
- Ask patient to complete the PDSS-2
- Review use of concomitant therapies including PD therapies
- Review inclusion/exclusion criteria to ensure patient still qualifies
- Randomize patient
- Perform MMIDI

- Ask patient to score the severity of EMO
- Ask patient to complete the ESS
- Ask patient to complete the NHQ Section 1. NHQ Section 2 should be completed by spouses or caregivers who are with the patients during the night at the same day. If no spouses or caregivers during the night, document it in the medical note and no need to complete NHQ Section 2.
- Ask patient to complete the SCOPA-Sleep
- Ask patient to complete the quality of life assessment (PDQ-8 and EQ-5D-5L)

- Dispense study medication to the patient to ensure the sufficient study medication until the next on-site visit with verbal instructions on how to take the medication. Remind the patient to take the study medication Pramipexole IR regularly three times per day with the third dose at 7-9 pm before bedtime or take study medication Pramipexole SR once daily at 7- 9 pm before bedtime. Additionally, remind the patient to bring the medication boxes (including all blank blister(s), unused and partially used study medication) back at the next scheduled on-site visit. The unused and partially used study medication will be returned to patients for treatment after drug accountability until the end of treatment. Study medication must be administered at the next day after randomization.
- Record AEs or follow-up on AEs continuing from the prior visit

- Schedule patient's next contact (telephone call, TC1) to study site one week later

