4.1.3 Method of assigning patients to treatment groups

After confirming that the patient meets all the eligibility criteria at Visit 2, the patient will be randomly assigned to SR or IR arm (with a randomization ratio of 1:1).

The randomization list will be carried out centrally using BI randomisation operator (ROP). Based on the randomization list, the external vendors will implement the assignment. The BI standard validated random number generating system will be used to generate the randomization list, which will be verified by an independent statistician who is not involved in the trial. The access to the randomization code will be supervised by the Clinical Trial Support Group. Any personnel directly involved in the conduct and analysis of the trial will have no access to the randomization schedule prior to the database lock.

The investigators will receive a manual describing how to communicate and implement the assignment with the support of the external vendor.

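### Visit 2 lists randomisation ahead of the only baseline ratings of ESS, NHQ, SCOPA-Sleep and PDQ-8, and no passage shown requires those ratings before allocation

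*Protocol*

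**What the plan says.** Section 6.2.2.1 of the protocol describes Visit 2 as a bullet list. It runs: vital signs, diary check, PDSS-2, concomitant therapies, "Review inclusion/exclusion criteria to ensure patient still qualifies", then "Randomize patient". After that come MMIDI, "Ask patient to score the severity of EMO", ESS, NHQ, "Ask patient to complete the SCOPA-Sleep", PDQ-8 (with EQ-5D-5L), and then dispensing with dosing instructions.

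Three other statements in that section bear on timing:

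- If the diary is not valid, "no other activities or ratings should be done, i.e. the patient is not eligible for baseline evaluation".
- For the caregiver part of the NHQ, "NHQ Section 2 should be completed by spouses or caregivers who are with the patients during the night at the same day".
- "Study medication must be administered at the next day after randomization".

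Section 4.1.3 says what must precede assignment: "After confirming that the patient meets all the eligibility criteria at Visit 2". It also mentions a manual on how assignment is communicated and implemented; that manual is not shown. Section 8.3.1 requires documented evidence for the inclusion and exclusion criteria before allocation. Section 4.1.5.1 states that there is no blinding, and section 8.7 that IRT is not used.

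**The concern.** A baseline is protected by randomisation only if it is rated before anyone who rates it can know the arm. ESS, SCOPA-Sleep, PDQ-8 and NHQ Section 1 are patient-rated, and NHQ Section 2 is caregiver-rated (section 5.1). If a patient or caregiver learns the arm and then fills in the form, expectation about the SR or IR formulation could shift the score differently in the two groups.

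The baseline is used twice: it is subtracted to form the change, and under sections 7.3.1 and 7.3.2 it enters the repeated measures model as a covariate. Analysis cannot restore a baseline that was taken after allocation. Section 3.2 relies on randomisation to limit bias in this open-label design, so the order of steps at Visit 2 matters more here than it would in a blinded trial.

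**Working it through.** No figure in the plan bears on this point, so the check is a comparison of passages, a count and an illustration.

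**1. Is Visit 2 the only baseline?** The flow chart schedules ESS, NHQ, SCOPA-Sleep and PDQ-8 at Visit 2 and not at Visit 1. The next ratings are at Visit 3 (Visit 5 for PDQ-8), on treatment. Visit 2 is the only baseline for all four.

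**2. Does another rule force the ratings before allocation?** Sections 4.1.3 and 8.3.1 do so only for what eligibility needs.

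- PDSS-2 is needed for inclusion criteria 5 and 6 and exclusion criterion 11, so it is forced before allocation.
- The EMO question is needed for inclusion criterion 7, so it is forced too, although its bullet stands after randomisation.
- ESS, NHQ, SCOPA-Sleep and PDQ-8 appear in no eligibility criterion, so they are not forced.

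The diary rule is the one explicit ordering rule at Visit 2. It makes ratings wait for a valid diary; it does not make randomisation wait for ratings.

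**3. Count over the nine secondary endpoints of section 2.1.3**

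| Group | Endpoints | Number |
|---|---|---|
| Only baseline listed after randomisation, no rule moving it earlier | NHQ, SCOPA-Sleep, PDQ-8, ESS | 4 |
| Affected only if the list is followed against sections 4.1.3, 5.1 and 8.3.1 | EMO change, EMO responder | 2 |
| Not affected: PDSS-2 is rated for eligibility; CGI-I and PGI-I have no baseline score | PDSS-2 responder, CGI-I, PGI-I | 3 |

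4 + 2 + 3 = 9. The change-from-baseline secondary endpoints are NHQ, SCOPA-Sleep, EMO, PDQ-8 and ESS, so the first group is 4 of those 5.

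**4. How a shifted baseline would carry through (illustration, on assumptions).** Let d be a difference between arms in the baseline caused by knowing the arm, and b the slope of follow-up on baseline. With later scores unchanged, the adjusted treatment difference moves by −b × d, and the unadjusted change score by −d. The protocol gives neither b nor d. For d = 1 point and b assumed between 0.3 and 0.7, the adjusted difference moves by 0.3 to 0.7 points, against 1 point unadjusted. Baseline adjustment thus reduces the error without removing it. Whether d differs from zero, and its sign, cannot be derived from the protocol.

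**5. The EMO bullet.** The baseline EMO rating is listed after randomisation. Inclusion criterion 7 uses the same question and must be documented before allocation. Section 5.1 also requires the rating within half an hour of waking and before the first anti-parkinsonian dose of the morning. The list does not say how a score made then reaches the site. These passages do not fit together as written.

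**The case against.** The strongest reply is that the lists in section 6.2 are not reliable sequences. At Visit 1 the eligibility review is listed before the safety bloods, pregnancy test and ECG on which exclusion criteria 7, 13, 14 and 24 depend. The flow chart prints randomisation above the diary review and PDSS-2, both of which must come first. The EMO bullet itself shows that a place after randomisation need not mean done after allocation. This stands: list order alone does not prove the order of conduct. Against it, PDSS-2 precedes randomisation at Visit 2 but sits between ESS and NHQ at Visits 3 to 7, which suggests it was moved forward on purpose and the other scales were not. And if the list is unordered, the gap remains, because a site that randomises first and then hands out the forms breaks no rule shown.

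A reader might go further and infer that these baselines are rated with the arm known. The protocol does not support that. Read as a sequence, the list puts dispensing and the arm-specific instructions after every questionnaire. No passage says when the patient is told the arm. Open-label means that the arm is not concealed; it does not fix when it is disclosed. The assignment manual may settle the timing, and the public text of the Visit 2 list has gaps, so a finding of absence covers only what is shown. The most exposed case is a caregiver who is not on site and completes NHQ Section 2 later the same day, possibly after dispensing.

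The stakes are also limited. SCOPA-Sleep asks about the previous month, which lies before allocation. All later ratings are open-label by design. Section 3.3 would allow another endpoint to become the Stage II primary under Scenario C, but the default there is to stop, and section 3.1 keeps Stage I patients out of Stage II.

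**Conclusion.** The concern holds in a limited form. A site that follows the Visit 2 list takes the only baseline of 4 of 9 secondary endpoints (4 of the 5 change-from-baseline ones) after allocation, and no passage shown prevents this. At that moment the patient or caregiver may know the arm; that they do know it is not established.

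The conclusion rests on the list being followed in order and on the unseen manual not setting a different one. The primary endpoint and the PDSS-2 responder rate are unaffected. The ratings still precede the first dose, so a drug effect on them is not in question. Section 7.2 makes Stage I descriptive. No size or direction of bias can be given. This is a cheap, worthwhile correction to the visit instructions, and it does not bear on the primary result. The EMO inconsistency is a separate documentation point and adds nothing to the count of four.

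**What to change.** - In section 6.2.2.1, list ESS, NHQ Section 1, SCOPA-Sleep and PDQ-8 before the randomisation bullet, and state that all patient-completed baseline ratings are finished before randomisation is requested.
- Have NHQ Section 2 completed before randomisation when the caregiver is on site. Otherwise keep the same-day rule and record that the form was completed after allocation.
- Reconcile the EMO bullet with inclusion criterion 7 and sections 4.1.3, 5.1 and 8.3.1, including how the score made on waking reaches the site.
- Check that the assignment manual says the same.

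The cost is one reordered checklist and one added instruction, a slightly longer visit before randomisation, and a few questionnaires from patients who then fail eligibility. No sample size figure changes. The endpoints whose only baseline is listed after allocation fall from 4 of 9 to none, apart from NHQ Section 2 forms completed off site, which would be identifiable.
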